CLINICAL EVALUATION OF CHAIRSIDE CAD/CAM LITHIUM DISILICATE FIXED PARTIAL DENTURES

Clinical Evaluation of Chairside CAD/CAM Lithium Disilicate Fixed Partial Dentures

Copyright 2013: This Clinical Investigation Protocol, or any part thereof, may neither be passed on to third parties nor may it be reproduced, stored in a retrieval system, or transmitted, in any form or by any means; electronic, mechanical, photocopying, recording, or otherwise, without prior permission of [name], University of Michigan, USA.

Page 2

1 Investigation Title

Clinical Evaluation of Chairside CAD/CAM Lithium Disilicate Fixed Partial Dentures

2 Investigators

[name] Clinical Professor

[name], MS Clinical Associate Professor

[name], MS Professor of Dentistry

[name], DDs, MS [name] of Dentistry

[name], MS Associate Professor of Dentistry

Department of Cariology, Restorative Sciences, and Endodontics School of Dentistry University of Michigan [name] U.S.A.

[contact] e-mail: [name] = [contact] [contact]

3 Sponsor

Ivoclar Vivadent, USA

4 Summary of Objectives and Design

This investigation will be a longitudinal clinical trial to study the clinical performance of lithium disilicate (emaxCAD/Ivoclar) for in-office, CAD/CAM generated, full contour fixed partial dentures (FPDs). The fixed partial dentures will be evaluated for clinical performance over a period of three years with an option to extend the study to five years.

5 Specific Aims

The specific aims of this project are:

Evaluate the longitudinal clinical performance of lithium disilicate (emaxCAD) in-office CAD/CAM full contour, fixed partial dentures over five years of clinical service.

Evaluate the clinical workflow for fabricating in-office CAD/CAM FPDs.

6 Significance of the Clinical Investigation

Lithium disilicate (emaxCAD/Ivoclar) has had well documented, long-term success for chairside CAD/CAM full contour single crown applications.^{1,2} It has been routinely used for clinical situations requiring high strength and is available in millable block form for single tooth restorations for both the E4D (D4D Technologies) and CEREC (Sirona Dental) chairside CAD/CAM systems. As the CAD/CAM software for the CEREC OmniCam has evolved, full contour, multi-unit restorations are now possible using lithium disilicate.

Pressable lithium disilicate (emax Press/Ivoclar) has been used in dental laboratories to fabricate 3 or 4 unit fixed partial dentures (FPD). Limited published long term results have been favorable.³ Lithium disilicate FPDs have been limited to replacing premolar or anterior teeth. Multi-unit emaxCAD blocks have been available for laboratory use for stack milling but unavailable for in-office use until recently. The coincidental development of the software capability for full contour FPDs and extended size millable blocks of emaxCAD make the in-office fabrication of full contour FPDs possible.

This three year, optionally five year, longitudinal clinical evaluation will evaluate the clinical effectiveness of using emaxCAD to fabricate in-office, full contour, fixed partial dentures.

Research Plan: Methods and Materials

7.1 Subjects

The patient population will be selected from current patients under clinical treatment at the University of Michigan Dental Clinics. Patients will be over 18 years of age, of either gender, and of any ethnic background. Each patient should have at least one missing premolar or anterior tooth that is appropriate for replacement with a fixed partial denture. The second premolar teeth will be the most distal tooth acceptable for inclusion in the study. Abutment teeth will have healthy periodontal status with at least a 1:1 crown:root ratio. Both abutment teeth must be asymptomatic prior to treatment. Endodontically treated teeth will be acceptable for abutments as long as nonmetallic cores can be placed to retain the FPD since the lithium disilicate will be bonded to the abutments.

No more than one FPD will be placed per patient. If a patient presents with more than one missing teeth acceptable for the study, premolar teeth will be included prior to anterior teeth. Each FPD will be three units and include only one missing tooth.

Exclusion criteria will include:

Sensitive teeth

Teeth with a history of direct or indirect pulp capping procedures

Patients with significant untreated dental disease to include periodontitis and rampant caries

Pregnant or lactating women

Patients with allergies to any of the materials to be used in the study

Patients unable to return for recall appointments

7.2 Ethics Approval and Informed Consent

The Health Sciences Institutional Review Board of the University of Michigan must review and approve the investigation protocol prior to initiating the study. Patients can be enrolled in the study as soon as the contract is completed and funding is provided. Patients who are eligible for the study will be screened by one or more of the investigators and the Clinical Research Coordinator and fully informed of the nature of the study and the need for long-term availability. Each patient who participates in the study will sign an informed consent agreement and the originals will remain at the University. Patients will be charged \$650 for each FPD. This will fund an incentive fund for patient recalls. As an incentive for patients to be available for the recall examinations, patients will receive \$50 for every yearly recall that they return to be examined as well as free parking. Patients will also receive free bitewing radiographs at the twoyear (and optionally the five year) recall appointments.

After admission to the study a subject may withdraw at any time for any reason. The right of each subject to withdraw and the right of each subject to confidential treatment of personal data will be respected at all times. The PI will record any subject's withdrawal and the reason(s).

7.3 Study Size

The study will include 30 patients each requiring a single FPD replacing a premolar or anterior tooth.

7.4 Baseline - Restoration Placement

Every patient will be evaluated with a clinical examination and periapical radiographs of the teeth to be included in the FPD. Once the patient is accepted into the study, a series of appointments will be made to complete the FPD.

1st Restorative Appointment

A pre-operative questionnaire will be completed jointly by the patient, Clinical Research Coordinator, and treating doctor (copy enclosed in Appendix). This will establish the baseline information from which to compare the responses at subsequent recall examinations. Abutment teeth to be restored will be tested subjectively as described in the Data Collections section to follow. The level of sensitivity will be recorded using a criterion-referenced rating scale. The use of the scale will be explained to the patient prior to beginning the evaluation. A Caries Risk Assessment will be completed for each patient at baseline based on the number of restorations the patient reports having received in the previous 12 months as well as the number of caries teeth planned to be restored over the next 6 months. Low Caries Risk will be scored for patients having 0 or 1 restoration placed in the previous 12 months or planned to be replaced due to caries. Moderate Caries Risk will be scored for patients having 2 or 3 restorations placed in the previous 12 months or planned to be replaced due to caries. And *High Caries Risk* will be scored for patients having 4 or more restorations placed in the previous 12 months or planned to be replaced due to caries. High caries risk patients will not qualify for the study due to the degree of uncontrolled dental disease that is present. The shade of the teeth to be restored will be determined prior to tooth preparation. A Classic Shade guide (Vita) will be used to determine the pre-treatment shade. Digital photographs of the dentition with the selected shade tab(s) will be taken and used as an aid in matching the desired tooth shade. Pre-treatment full arch diagnostic impressions may be made for case evaluation and as an aid in fabricating the temporary FPD should the need arise.

2nd Restorative Appointment - Preparation

All restorative procedures will be performed under standard local anesthesia with no increased risks incurred by patients participating in the study beyond those involved in routine dental treatment. An Isolite2 System (Isolite) will be used to isolate the teeth for cavity

preparation, optical imaging, and cementation of the restorations. The abutment preparation will be consistent with the principles for an all-ceramic crown. The crown preparation will be tapered 6-8 degrees towards the occlusal. Occlusal reduction will be 2.0 mm over functional cusps and at least 1.5 mm over nonfunctional cusps and the central fissure area. And the margin will be a rounded internal shoulder design of at least 1.2 mm axial depth without a bevel. The crown margins will be placed at the free gingival margin unless prior restoration, caries, or tooth fracture dictates margin placement subgingivally. If sufficient tooth loss is present to necessitate a core, a composite resin (Multi-core/Ivoclar) will be used. If in the judgment of the operator, less than 1 mm of dentin thickness remains over the pulp, a glass ionomer base may be selectively placed prior to completing the preparation.

FPD Fabrication

After the abutment crown preparations have been completed, gingival retraction will be achieved with a combination of retraction cord, hemostatic agent, and a diode laser as required for the case. The quadrant will be isolated from moisture using an Isolite 2 unit. The CEREC OmniCam (Sirona Dental) will be used to record the preparation quadrant, opposing quadrant, and facial bite registration.

If the case requires a temporary FPD, a bisacrylic material (Telio C&B/Ivoclar) will be used to fabricate a temporary FPD that will be cemented with a eugenol-free temporary cement. The digital impression will be used in the CEREC 4.21 software program for the full contour design of the FPD. The designed FPD will be milled in a MCXL milling unit (Sirona Dental) at fast milling speed.

The milled emaxCAD FPD will be tried in using silicon fit checking material (Fit Checker/GC Amer) and adjusted for delivery. Alternatively, the milled FPD will be tried-in on a replica model of the preparations and adjusted for delivery. The FPD will be crystallized in a porcelain oven under vacuum firing following Ivoclar's recommendations. Esthetic characterization and/or glazing of the FPD will also be done simultaneous with the crystallization process as the esthetic needs of the case dictates. Surface polishing post-crystallization will be done with diamond impregnated polishers, brushes, and diamond polishing paste. Both proximal connectors will be measured in the faciolingual and occlusocervical directions and recorded. Each connector should be no less than 16 mm².

3rd Restorative Appointment - FPD Delivery

Once the FPD is ready is for cementation, the internal surface of all abutment crowns will be etched for 20 seconds with 4.9% HFl acid (Ceramic etchant/Ivoclar), rinsed thoroughly, and dried. A silane coupler will be applied for 60 seconds (Monobond Plus/Ivoclar) and gently dried. All FPDs will be cemented with the most current formulation of a self-etching, dual-cure resin cement (MultiLink Automix/Ivoclar) following the manufacturer's instructions. The FPD will be inserted and the excess cement will be removed. Each abutment of the FPD will be light cured for 20 seconds from the facial, lingual and occlusal for a total cure of 2 minutes.

Finishing and polishing will be initiated after visible light curing of the luting agent. A series of diamond finishing burs, rubber abrasive points and cups, finishing strips, and diamond polishing paste will be used for removal of excess cement and final adjustment of the occlusion.

Data Collection

8.1 Post-Operative Sensitivity

All patients will be asymptomatic prior to initiating the abutment preparations so the baseline is "no sensitivity". To evaluate the immediate post-operative sensitivity, patients will be contacted by telephone once a week after the initial appointment for four weeks or until the FPD is reported asymptomatic. A criterion-referenced rating scale will be used to measure sensitivity. The phone interview will be used as a follow-up procedure to minimize recall loss as the patient is not required to return to the clinic. During the phone interview a criterion-referenced rating will be made of functional tooth sensitivity using the following scale. Patients will only be asked to return for an evaluation if they are having continued discomfort or any indication of premature occlusal contact.

Sensitivity Criteria:

- 1= No sensitivity is experienced at anytime
- 2= Slight sensitivity is experienced occasionally but it is not uncomfortable
- 3= Moderate sensitivity is experienced intermittently and it is noticeably uncomfortable
- 4= Severe discomfort is noted routinely with cold or pressure stimulation

8.2 Clinical Evaluation

Two independent evaluators will examine all FPDs in the study. Clinical evaluations will be made at baseline (the appointment the FPD is cemented), six months, one year, two years, three years, and optionally at four years, and five years using written criteria based on modified USPHS criteria for margin discoloration, margin adaptation, proximal contact, recurrent caries, surface finish, connector fracture, and crown fracture (see Appendix for criteria description). Disagreements in evaluations will be discussed between the evaluators and a consensus judgment will be reached and recorded for every criteria. Gingival health adjacent to the abutments and control teeth will be evaluated with a Gingival Score (Loe & Silness Index, 1963) and a Plaque Score (Silness & Loe Index, 1964).

Intraoral digital color images at a 1:1.5 magnification will be taken to document preoperative, tooth preparation, and post-operative conditions. Facial and occlusal views of the tooth will be documented for both the pre-operative and post-operative conditions.

A postcementation quadrant impression will be made of the midfacial margin of each abutment and the opposing teeth in a polyvinyl siloxane material and casts will be poured in an enhanced stone. Casts will be made at the baseline, 6 months, 1 year, 2 year, and 3 year, and optionally at the 4 year, and 5 year recall visits. Bite-wing radiographs and periapical radiographs of each test tooth will be available preoperatively and at the two year and optionally at the five year recall.

8.3 Data Management

Case Report Form (CRF)

Data will be entered in the Case Report Form (CRF) by the investigator or prior assigned persons at the study center. The entries will be made with blue ball-point pen. In case of necessary corrections, the wrong entry will be crossed out and the new entry will be written beside it. No erasure is allowed for corrections. Changes or corrections will be dated and initialized by the investigator or assigned person(s). The documentation of each patient visit (baseline and recalls) must be signed and dated by the conducting investigator.

Copies of the completed CRFs and Adverse Events/Incident Reports will be retained together with the investigator's study file for a period of 10 years after completion of the study at Page 9

the study center. Data entry will be done by the Clinic Study Coordinator of the Cariology, Restorative Sciences Clinical Research Unit.

9 Statistical Analysis

After the clinical evaluation data is collected for baseline and each recall, the clinical ratings will be entered into a statistical management program and appropriate non-parametric tests will be run to verify significant differences. A Wilcoxon Sign Rank test will be used to determine significant differences in the change of ratings from baseline to a given time period. Each criterion-referenced category will be analyzed independently. At any given time period, significant differences in clinical evaluation ratings will be determined.

10 Project Time Line

The recruitment of patients and clinical placement of restorations will begin immediately upon approval and funding of the project. It is anticipated to take 8-10 months to recruit and place the restorations required for the study.

11 Equipment

All instrumentation required for placement and clinical evaluation of the restorations is available through the Research Clinic of the Department of Cariology, Restorative Sciences, and Endodontics at the University of Michigan School of Dentistry. Additional measurement instrumentation to include measuring microscopes, scanning electron microscope, computer analysis, and intraoral imaging equipment is available within the School of Dentistry.

12 Facilities

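### Section 9 plans no FPD-level failure or survival estimate: its one named test, run by criterion and visit, gives no failure share or interval, and no rule covers replaced FPDs

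*Combined protocol and SAP*

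**What the plan says.** Section 5 gives the first aim as "Evaluate the longitudinal clinical performance of lithium disilicate (emaxCAD) in-office CAD/CAM full contour, fixed partial dentures over five years of clinical service". Section 6 describes a three-year, optionally five-year, study in which the "longitudinal clinical evaluation will evaluate the clinical effectiveness of using emaxCAD" for in-office FPDs. On size, Section 7.3 says "The study will include 30 patients each requiring a single FPD"; Section 7.1 allows one FPD per patient. There is no comparison group.

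Section 8.2 has two evaluators rate each FPD at baseline and at every recall, by consensus, on "margin discoloration, margin adaptation, proximal contact, recurrent caries, surface finish, connector fracture, and crown fracture", with reference to the Appendix. Four Appendix ratings state that replacement is needed: Delta on abutment fracture, on connector fracture and on pontic fracture, and Charlie on caries.

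Section 9 says that "appropriate non-parametric tests will be run to verify significant differences", that "A Wilcoxon Sign Rank test will be used to determine significant differences in the change of ratings from baseline to a given time period", and that "Each criterion-referenced category will be analyzed independently". It adds that significant differences will be determined at each time period. On losses, Section 7.2 says "After admission to the study a subject may withdraw at any time for any reason", and that withdrawals and their reasons are recorded.

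No section mentions a failure or survival estimate, a confidence interval, censoring, a definition of failure across criteria, or what happens in the analysis to an FPD that has been replaced.

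**The concern.** In a single-arm study of a restoration, a natural question is how many of the restorations were still in service at three years and how well that share is known. The plan collects the ratings needed to answer it but specifies no analysis that does. There are three gaps.

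1. A signed-rank p-value for change from baseline is neither a share nor an interval, and it can be the same whether the affected FPDs were retained or lost.
2. Because criteria are analysed one at a time, failures of different kinds in different FPDs are never added together.
3. Without a rule for replaced FPDs, later paired comparisons may describe survivors only, or may include a new restoration rated afresh.

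At stake is whether the main performance result is fixed in advance or assembled after the ratings are known.

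**Working it through.** The plan gives only a study size (30) and no alpha, power, failure rate or precision target, so there is no stated figure to reproduce. The examples below show how the named test behaves. They are not forecasts of failure.

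**Inputs from the documents.** 30 patients with one FPD each (Sections 7.1 and 7.3); ordered ratings Alpha to Delta for connector and abutment fracture (Appendix); signed-rank test by criterion and visit (Section 9).

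**Assumptions, not in the documents.** Two-sided 0.05; all 30 FPDs rated Alpha at baseline; 30 pairs at the visit; changes of equal size within a criterion.

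**Formulas.** With k FPDs worsening and 30 − k unchanged:
- Exact two-sided p, unchanged pairs dropped: 2 × (1/2)^k, whatever the size of the changes.
- Normal approximation for equal changes: z = √k.
- Failure share: k/30 with an exact (Clopper-Pearson) 95% CI. For k = 0 the upper limit is 1 − 0.025^(1/30) = 11.6%.

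**Example 1: same p-value, different failure share.** Take k = 6 on connector fracture.
- Exact p = 2 × (1/2)^6 = 0.031. The approximation, z = √6 = 2.45, gives p = 0.014, or 0.020 with continuity correction.
- All six at Bravo: 0/30 at replacement level, 0% (95% CI 0% to 11.6%).
- All six at Delta: 6/30, 20% (95% CI 7.7% to 38.6%).
- The p-values are identical because six one-grade changes and six three-grade changes receive the same ranks.
- If three FPDs move one grade and three move three grades, the uncorrected approximation becomes 0.024 instead of 0.014. The exact p remains 0.031.

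**Example 2: failures split across criteria.** Three connector Deltas and three abutment Deltas occur in six different FPDs.
- FPD level: 6/30 = 20% (95% CI 7.7% to 38.6%).
- Each criterion has k = 3:

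| Version of the test | Two-sided p |
|---|---|
| Exact | 2 × (1/2)^3 = 0.25 |
| Approximation, z = √3 = 1.73 | 0.083 |
| With continuity correction | 0.149 |
| Zero changes ranked, without / with correction | 0.083 / 0.087 |

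- One-sided, the uncorrected approximation gives 0.042, and ranking zeros with correction gives 0.043. Both fall just below 0.05. Section 9 states neither sidedness nor alpha.

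**Example 3: replaced FPDs.** Suppose the six FPDs of example 2 are replaced and leave the paired data, and the other 24 are unchanged. The next visit then has 30 − 6 = 24 pairs with no change on either criterion, while the cumulative failure share is still 6/30 = 20%.

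**Precision that the added summary would show.** 0/30 failures: upper limit 11.6%. 3/30 = 10%: 95% CI 2.1% to 26.5%.

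**The case against.** The strongest reply is that the documents name no survival endpoint, success threshold or failure-rate claim. Section 8.2 expresses performance as ratings by criterion, and Section 9 analyses those ratings. That stands: Section 9 contradicts no stated endpoint, and giving survival a central place is a judgement about what best answers the aim.

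A reader might infer that the study could not reveal how many FPDs failed. The documents do not support that. Consensus ratings are recorded for every criterion at every visit, four grades already state that replacement is needed, adverse event and incident reports are retained (Section 8.3), and withdrawals are recorded. A count out of 30 can be read from these. What remains open is how to combine the grades, how to treat replaced FPDs, and how to state precision.

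A reader might also infer that the split failures of example 2 are non-significant however the test is run. That is true only two-sided.

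Nor should connector Bravo be read as trivial. The Appendix calls it a connector fracture, without a missing piece or mobility. The contrast with Delta is only that Bravo does not state a need for replacement.

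Finally, the open-ended mention of non-parametric tests could be said to leave room for a survival method. It refers to tests of differences in ratings, and fixes no estimate, event or censoring rule.

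**Conclusion.** The point holds as an omission worth correcting. Followed as written, Section 9 produces p-values by criterion and visit, with no FPD-level failure share, no interval and no rule for replaced FPDs. In the examples, a 20% replacement-level share either shares its p-value with a 0% share or is split into two tests with two-sided p of 0.083 to 0.25. These figures rest on the assumed two-sided 0.05, all-Alpha baseline, complete pairs and equal changes. The omission itself rests on none of them. The by-criterion ratings remain useful results, and the data collection is largely adequate. The gap lies in the pre-specified analysis.

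**What to change.** In Section 9, add:

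- **Estimate.** FPD survival at three years, and at five if the study is extended, over all cemented FPDs with a 95% CI. Use Kaplan-Meier, or an exact binomial interval if follow-up is complete.
- **Event.** The first of any replacement-level Appendix rating (Delta on abutment, connector or pontic fracture; Charlie on caries), or removal or replacement of the FPD for any reason. Removal is not an Appendix criterion, so confirm that it is captured, for example in the incident reports, or add one line to the case report form.
- **Dating and censoring.** Date an event at the visit or report where it is first recorded, and state that events found at recall are interval-censored between visits. Censor losses and withdrawals at the last visit.
- **Replaced FPDs.** A failed FPD stays a failure at later visits on the criterion on which it failed. That alone leaves the other criteria describing survivors, so label later results on those criteria as describing FPDs still in service, and show them beside the cumulative failure count.
- **Wilcoxon tests.** Keep them as supporting results.

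The Section 8.2 list omits pontic fracture, but also color match and sensitivity. If it is edited, align the whole list with the Appendix.

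The cost is rewording and possibly one form line, with no extra patients or visits. The downside is a visibly wide interval: no failures in 30 would still be compatible with a failure rate of up to 11.6%, and three failures with one of up to 26.5%.

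### The signed-rank test named in Section 9 is a poor summary of post-operative sensitivity: measured from Section 8.1's floor baseline, its exact p-value ignores how severe the sensitivity is

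*Combined protocol and SAP*

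**What the plan says.** Section 9 (Statistical Analysis) names a single test: "A Wilcoxon Sign Rank test will be used to determine significant differences in the change of ratings from baseline to a given time period". It adds: "Each criterion-referenced category will be analyzed independently". It also refers in general terms to suitable non-parametric tests without naming any. It gives no significance level, no confidence interval and no summary by grade.

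Section 8.1 (Post-Operative Sensitivity) describes weekly telephone ratings for four weeks, or until the restoration is reported free of symptoms. The scale is criterion-referenced and runs from "1= No sensitivity is experienced at anytime" to "4= Severe discomfort is noted routinely with cold or pressure stimulation". On the starting point it says "All patients will be asymptomatic prior to initiating the abutment preparations so the baseline is" the no-sensitivity level. Section 7.1 enforces this at entry: "Both abutment teeth must be asymptomatic prior to treatment".

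Two other places bear on the point. The appendix lists Sensitivity among the clinical evaluation criteria, with the same four levels labelled Alpha to Delta. Section 8.2 sets the baseline for the clinical evaluations at the cementation appointment, which comes after preparation.

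**The concern.** A signed-rank test is useful when changes can go either way and their sizes differ. Measured from the Section 8.1 baseline, neither feature does any work. No patient can improve, so a null of change symmetric about zero has little meaning. With every change in the same direction, the ranks that carry severity also drop out of the exact p-value.

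Sensitivity is rated more often than any other outcome in the protocol, on a scale built to separate symptoms that are not uncomfortable from severe discomfort. The useful result from a single group of 30 is how many patients had noticeable or severe discomfort, and how precisely that is known. The named test gives neither, and it can give a smaller p-value for a milder set of results.

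**Working it through.** **Inputs.** There are 30 patients with one restoration each (Section 7.3: "The study will include 30 patients each requiring a single FPD replacing a premolar or anterior tooth"). Baseline is grade 1 and the scale runs from 1 to 4 (Section 8.1), so change can only be 0, +1, +2 or +3. The plan has no figure of its own to reproduce: 30 is given without a derivation, and no expected sensitivity rate is stated. A two-sided level of 0.05 is assumed below. The case counts are illustrations and assume all 30 patients are observed.

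**Exact test.** Let k be the number of patients with any sensitivity. Zero changes are dropped and the other k are all positive, so W− = 0 and W+ = 1 + 2 + … + k = k(k+1)/2. Tied grades share mid-ranks, which leaves the sum unchanged. Of the 2^k equally likely sign patterns, only all-positive and all-negative are as extreme as this, so

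p = 2 × 0.5^k.

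The grade does not appear. For k = 5, p = 2/32 = 0.0625; for k = 6, p = 2/64 = 0.031.

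**Large-sample version, tie-corrected, no continuity correction.** Z = (W+ − Σr/2) / √(Σr²/4), where r are the mid-ranks. If all k patients share one grade, each mid-rank is (k+1)/2, so

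Z = [k(k+1)/4] / [(k+1)√k/4] = √k, whatever the grade.

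With mixed grades Σr stays the same but Σr² rises, so Z falls. Three slight plus one severe has mid-ranks 2, 2, 2, 4: Σr = 10, Σr² = 28, and Z = 5/√7 = 1.890.

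| Patients with sensitivity | W+ | Exact p | Z | Large-sample p |
|---|---|---|---|---|
| 3 severe | 6 | 0.25 | 1.732 | 0.083 |
| 4 slight | 10 | 0.125 | 2.000 | 0.0455 |
| 3 slight + 1 severe | 10 | 0.125 | 1.890 | 0.059 |
| 5 slight | 15 | 0.0625 | 2.236 | 0.025 |
| 5 severe | 15 | 0.0625 | 2.236 | 0.025 |
| 6 slight | 21 | 0.031 | 2.449 | 0.014 |
| 3 slight + 3 severe | 21 | 0.031 | 2.251 | 0.024 |

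Six slight cases therefore give a smaller p than five severe cases in both versions. Where 0.05 is crossed depends on the version: between k = 5 and k = 6 for the exact test, and between k = 3 and k = 4 for this approximation. Ranking the zeros as well (Pratt) leaves six slight against five severe at 0.014 against 0.025, and mixed grades then hardly move the p-value (three slight plus one severe 0.0456, four slight 0.0455).

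**Counts with exact (Clopper-Pearson) 95% intervals for the same data.**
- Five severe: 5/30 = 16.7% at grade 3 or more (5.6% to 34.7%).
- Six slight: 6/30 = 20.0% at grade 2 or more (7.7% to 38.6%), and 0/30 at grade 3 or more (upper limit 11.6%).

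These show the difference that the test hides.

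**The case against.** The strongest reply concerns scope. Section 9 never mentions sensitivity. Its opening sentence concerns clinical evaluation ratings at baseline and recall; the list of rated criteria in Section 8.2 omits sensitivity; and a weekly telephone call is not a recall visit. On that reading the signed-rank test does not reach the telephone scores, and the reversal shown above does not arise. This reading is possible. The broader one is more natural, because Section 9 takes in every criterion-referenced category, Section 8.1 describes its scale in those terms, and the appendix lists Sensitivity among the criteria. The narrower reading does not rescue the plan either, since it leaves the telephone scores with no named analysis.

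A second reply is that the floor depends on the baseline. If the appendix Sensitivity item is rated at recalls against the Section 8.2 cementation baseline, some patients could start above the floor and improve. That stands: the argument applies to change from the Section 8.1 baseline only, and the documents do not say which baseline governs the appendix item.

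A third is that severe cases have other routes into the record. Patients with continued discomfort are asked to return, adverse event reports are kept, and nothing in Section 9 forbids a table of grades. That also stands. The plan does not suppress severity; it does not commit to reporting it.

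**Conclusion.** The concern holds as a matter of poor fit between test and outcome. If the signed-rank test is applied to change from the Section 8.1 baseline, its exact p-value counts patients with any sensitivity and ignores grade. Five severe cases (0.0625) then look like weaker evidence than six slight ones (0.031). That ordering needs no significance level; calling one significant and the other not rests on the assumed 0.05 and on the exact test.

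Three stronger readings are not supported:
- A reader might infer that the signed-rank test is the only analysis sensitivity can receive. It is the only named test, but Section 9 also leaves room for others and does not name this outcome.
- A reader might infer that severity never affects the p-value. That is true of the exact test. In the tie-corrected approximation mixed grades do enter, perversely (0.0455 for four slight, 0.059 for three slight plus one severe).
- A reader might infer that severe discomfort would go unreported, or that a study decision turns on this p-value. The stated aims are clinical performance and workflow, and no decision rule is given.

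The change is worth making because it is cheap and uses scores already collected.

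**What to change.** In Section 9, replace the signed-rank test for the Section 8.1 scores with a summary of each patient's worst score over the call period:

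- Report the number and percentage of patients at each worst grade, and the percentages with a worst score of 2 or more and of 3 or more, with exact (Clopper-Pearson) 95% intervals.
- Use as denominator all patients with a cemented restoration and at least one call, and state how many had no call.
- If counts by week are also shown, carry patients whose calls ended because they were asymptomatic as grade 1 and list missed calls separately. Otherwise the later weeks contain mainly patients who still have symptoms.
- State whether the Section 8.1 pre-preparation or the Section 8.2 cementation baseline applies to the appendix Sensitivity item, and summarise that item by grade counts at each recall.

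The cost is a few sentences in Section 9 and no new data. Sensitivity loses its p-value, and the intervals are wide at 30 patients: the 5/30 interval above spans about 29 percentage points (34.7 − 5.6 = 29.1). That width is a fair statement of what a study of this size can show.
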